#### **Funding:**

The Tobrisk-CoV study is funded by NordForsk (project number 105544)

## **Background**

The coronavirus disease (COVID-19) pandemic, caused by severe acute respiratory syndrome coronavirus 2 (SARS-CoV-2), has caused more than 470 million confirmed cases of COVID-19, and more than 6 million deaths around the world by March 25, 2022 (WHO, 2022). Since the beginning of the COVID-19 pandemic, several factors have been attributed to increasing the risk of infection and adverse outcomes of the COVID-19 disease. Among these factors, the relationship between tobacco use and COVID-19 infection and adverse disease outcomes remained controversial as studies kept reporting mixed findings. Early studies reported what seemed to be a protective effect of tobacco use on COVID-19 infection (Haddad et al.; Jiménez-Ruiz et al., 2020), or hospitalizations due to COVID-19 (Farsalinos et al., 2020; Neira et al., 2021). A more recent ongoing living rapid review, this time including a larger selection of studies with different study designs, found that smokers are at reduced risk of SARS-COVID-19 infection compared to non-smokers (Relative risk 0.67, 95% Credible interval 0.60-0.75) (Simons et al., 2021). These findings opened the way for speculations and hypotheses on the potential mechanisms behind this protective role. However, results from most of these studies may be affected by selection bias as they reported findings from clinical samples or bias due to confounding as the structure of these published data permitted only univariate analysis.

Results from studies that suffer from selection bias or bias due to confounding should be handled with caution as they may undermine years of public health education against tobacco use, a major cause of morbidity and mortality worldwide. Moreover, the role of tobacco use in disease progression such as disease requiring hospitalization, ICU, and death remains unclear as most of the previous studies focused more on the association between tobacco use and the risk of infection, but not the adverse outcomes. These facts call for studies that ensure addressing any knowledge gap on the relation between tobacco and COVID-19 by taking into consideration 1) decreasing the risk for confounding and selection bias; 2) increasing precision

through a higher sample size, 3) further investigating the association between tobacco use and adverse disease outcomes. In most Nordic countries, the profile of tobacco use in the underlying populations allows the analysis of several types of tobacco use e.g. cigarette smoking and smokeless tobacco (snus) use, enabling further insights into the potential role of nicotine in the association between tobacco use and COVID-19. The use of smokeless tobacco is highly prevalent (even exceeding the prevalence of smoking among men in Sweden and Norway), which will allow us to disentangle a potential role of nicotine in the association between tobacco use and COVID-19.

The aim of this study is to examine the associations between tobacco use, COVID-19 infection, and adverse disease outcomes by using pooled population-based data from three Nordic countries, adjusting for potential confounders. The population-based nature of the samples minimizes selection bias. Using a pooled analysis will accrue a large sample size and increase the potential for well-powered sub-groups analyses.

## **Methods**

### **Setting and study design**

This is an observational study of pooled population-based samples in three Nordic countries. Country-specific data has already been analysed in previous studies in Sweden ([name], 2021), Finland ([name] et al., 2021), and Norway ([name] et al., 2016). We will use the national personal number assigned to every resident in these three countries at birth or at immigration to obtain information on diagnoses of COVID-19 and adverse outcomes among individuals in these cohorts through record-linkage with regional and national databases.

## **Data Sources**

We will pool data from three Nordic countries, Sweden, Finland, and Norway. Briefly, Swedish data comes from a historical cohort of 424,386 clients of public dental clinics aged 23 and older in the Stockholm region with inception between October 2015 and January 2020, with follow-up from February 2020 to December 2020. In Sweden, the public dental clinics (Folktandvården, FTV) provide routine preventive visits (oral check-ups) to all residents who choose to receive care in these clinics. At each health check-up smoking and snus use are ascertained as past use, current use, and amount of current use. The national personal numbers assigned to every resident in Sweden at birth or at immigration will be used to obtain information on diagnoses of COVID-19 and of other diseases through record-linkage with regional health care registers. Demographic information will be extracted through record-linkage with the register of the total population of the Stockholm region held by Statistics Sweden.

The Finnish data will come from three pooled cross-sectional national health surveys in Finland (FinSote 2018-2020) of 44,199 participants aged 20 and older. The study samples included permanent residents in Finland from the FinSote surveys 2018, 2019, and 2020. The unique personal identifier assigned to all Finnish residents will be linked to the Communicable Diseases Registry to obtain information on diagnoses of COVID-19, to the Care Register for Health Care (HILMO) to obtain information on hospital admissions due to COVID-19, and to Statistics Finland Mortality Data to obtain information on deaths. Data on some sociodemographic characteristics will be also obtained from the Digital and Population Data Services Agency.

The Norwegian data will be based on the Norwegian Mother, Father and Child Cohort Study (MoBa) ([name] et al., 2016), and the Norwegian Influenza Pregnancy Cohort (NorFlu) (Laake, 2018), with linkages to the Norwegian Surveillance System for Communicable Diseases (MSIS), the Norwegian Immunisation Registry (SYSVAK), and the Norwegian Population Registry. MoBa is a nation-wide population-based cohort consisting of 280 000 participants, where

parents were recruited during pregnancy from 1999 to 2008, while NorFlu is a pregnancy cohort consisting of 9 000 participants recruited in Oslo and Bergen during the swine flu pandemic in 2009-2010. Since March 2020, cohort participants have been regularly invited to answer electronic questionnaires. In June 2020 and January 2021, participants were asked to report current smoking. Questions about snus and other tobacco use were asked in January 2021 only. COVID-19 diagnoses are obtained from registry data (MSIS) based on PCR confirmed SARS-CoV-2 infection. Demographic information is extracted from the registries via linkage to the existing cohort databases. For the purpose of this study, all subjects who died before the onset of the pandemic (February 2020) in the three countries will be excluded from the analysis.

We developed a harmonization protocol to create a comparable dataset. The harmonization process started with identifying all possible variables to be used in the pooled analyses. We then identified common variables across countries, and only variables available in at least 2 countries will be included in the pooled analysis. Each country provided the format on which these variables were stored in their respective datasets. Finally, we elaborated a document describing the format for the harmonized variables. The principle of harmonization was to create variables with a minimum common format. The harmonized variables list is as follows:

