## **Outcome Variables**

The study will include five outcomes: any diagnosis of COVID-19, hospital admission for COVID-19, length of hospital stay for COVID-19; intensive care use due to COVID-19, and death attributable to COVID-19. The follow-up period for all outcomes was from February 2020 until December 2020.

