***Date variables***

1. *Year of latest assessment of cigarette smoking*

Format: YYYY

2. *Year of latest assessment of snus use*

Format: YYYY

3. *Date of COVID-19 Diagnosis*

Format: DD/MM/YYYY

4. *Date of Hospital Admissions due to COVID-19*

Format: DD/MM/YYYY

5. *Date of Intensive Care Admission due to COVID-19*

Format: DD/MM/YYYY

6. *Date of hospital discharge*

Format: DD/MM/YYYY

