### **Statistical analysis**

Risk ratios (RR) and their corresponding 95% CI for COVID-19 infection, hospitalization, ICU, or death due to COVID-19 will be estimated through generalized linear models (GLM). We will use the Poisson family with robust standard errors and the maximum likelihood optimization algorithm to estimate the relative risk of a confirmed COVID-19 case, hospital admission, ICU, or death due to COVID-19 (Zou, 2004). First, adjusted Poisson regression (Zou, 2004) will be applied to assess the influence of exposure (smoking or snus) on the study's outcomes. If we assume that  $y_{ij}$  is the observed binary outcome (COVID-19 infection, hospital admission, ICU, or death due to COVID-19) for subject  $i$  in country  $j$ , the specification and the equation of the Poisson model is as follows:

$$\log(p_{ij}) = \beta_0 + \beta_1 X_{1ij} + \sum_k^R \beta_k X_{ijk} \quad (1)$$

where  $p_{ij}$  is the probability of the outcome  $y_{ij}$ ,  $X_{1ij}$  is the exposure (smoking/snus),  $\beta_0$  is the intercept,  $\beta_1$  is the regression coefficient corresponding to the exposure,  $X_{ijk}$  represents the subject's values of  $R$  covariates, and  $\beta_k$  is a regression coefficient corresponding to each covariate. Exponentiating  $\beta_1$  gives the corresponding relative risk, RR.

We will then apply a multilevel regression (Goldstein, 1995) which assumes that each country has its own COVID-19 infection probability, and this varies from one country to another. This will be the primary analytical model. In this multilevel model, the Poisson regression for COVID-19 infection will include an additional term  $u_j$ , which is the country-level random effects as a predictor variable:

$$\log(p_{ij}) = \beta_0 + \beta_1 X_{1ij} + \sum_k^R \beta_k X_{ijk} + u_j \quad (2)$$

In this model, the probability depends on the value of the random effects  $u_j$  which is the totality of unmeasured country-level variables that predict COVID-19 infection and are uncorrelated with the individual variables in the model.

As a secondary analysis, we will use a negative binomial count model (Hilbe, 2011, 2014) to assess inpatient length of stay (i.e. the cumulative number of days of hospitalization) as a measure of disease severity among tobacco users compared to non-tobacco users.

We will carry out stratified analyses by sex, age, education, and time period.

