We will carry out three sensitivity analyses. First, we will analyse the data adding tobacco-related comorbidity and employment as additional confounders with data from Sweden and Norway. Second, we will analyse only data prospectively collected to explore the influence of information bias. For this purpose, we will include data from Sweden and Finnish data from 2018 and 2019. This data will be analyzed with Cox proportional hazards models with the same specifications as the primary analysis. We will use time in study as the timescale. Participants will be censored due to end of follow-up or the occurrence of the event.

Third, for death of COVID-19, we will also include a competing risk analysis to take right-censoring due to a death non-attributable to COVID-19 into account. Competing risk means that a subject can experience one of a set of different events during the study period. Accordingly, the use of traditional methods of survival analysis, such as the Kaplan-Meier survival function, will result in incidence estimates that are biased upward, irrespective of the independence between the competing events (Austin et al., 2016; Berry et al., 2010; Kim, 2007; Southern et al., 2006). Instead, we will use two models to fit a regression in the presence of competing risk, the cause-specific hazard modeling and the sub-distribution hazard modeling (Austin et al., 2016). The cause-specific hazard function implies the instant rate of occurrence of a specific event in subjects who have not experienced yet any of the different types of events (Andersen et al., 2002; Austin et al., 2016). If we consider two types of events, death due to COVID-19 causes and death due to non-COVID-19 causes, then the cause-specific hazard of COVID-19 death implies the instant rate of COVID-19 death in subjects who have not yet experienced

either event (Austin et al., 2016). In the cause-specific hazards regression model, we will model the effect of covariates by using the traditional Cox proportional hazards model after censoring individuals with competing events at the time of their occurrence.

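### Norwegian snus use is recorded after every outcome in the primary model, and no rule puts Norwegian smoking (or Finland 2020) status before the outcome

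*Combined protocol and SAP*

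**What the plan says.** **Outcome window.** Outcome Variables states: "The follow-up period for all outcomes was from February 2020 until December 2020".

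**Norwegian exposure.** Data Sources states: "In June 2020 and January 2021, participants were asked to report current smoking". It adds: "Questions about snus and other tobacco use were asked in January 2021 only". Exposure Variables defines current smoking and current snus use by reported daily or occasional use. It names neither a questionnaire nor a reference date.

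**Dates held.** Date variables lists "Year of latest assessment of cigarette smoking" and "Year of latest assessment of snus use", both as a year only. Diagnosis, admission, intensive care and discharge are held to the day.

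**Primary model.** Statistical analysis says of the multilevel Poisson model on the pooled data: "This will be the primary analytical model". The only exclusion tied to a date is death before February 2020 (Data Sources).

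**Planned check.** Among the sensitivity analyses: "Second, we will analyse only data prospectively collected to explore the influence of information bias". It continues: "For this purpose, we will include data from Sweden and Finnish data from 2018 and 2019". This check uses Cox models.

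**The concern.** A current-use answer given after an infection can be altered by that infection. If infected users stop more often than uninfected users before they answer, the Norwegian RR moves towards apparent protection. If uninfected users stop more often, it moves towards apparent harm. If both stop equally, a true null stays null.

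This touches the purpose of the study. The Background attributes earlier protective findings to possible bias and relies on snus to separate out a role for nicotine. Norwegian snus is the component in which no answer precedes any outcome. For deaths the problem is structural and needs no assumption about stopping: from the January 2021 questionnaire, Norway supplies only survivors to the snus analysis.

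The plan limits its prospectively collected data to Sweden and Finland 2018 and 2019. It thus treats Norway and Finland 2020 as not prospective, yet nothing removes either from the primary model.

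**Working it through.** The plan gives no event counts, prevalences, power or Norwegian response numbers, so there is no stated figure to reproduce. The check has two parts.

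**1. Calendar order (from the documents)**

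The window, February to December 2020, is 11 calendar months.

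| Norwegian exposure | When asked | Outcome months wholly before the answer | Full outcome months after it |
|---|---|---|---|
| Snus | January 2021 | 11 of 11 | 0 |
| Smoking, June answer | June 2020 | 4 of 11 (February to May), plus part of June | 6 (July to December) |
| Smoking, January answer | January 2021 | 11 of 11 | 0 |

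Swedish inception runs from October 2015 to January 2020, so Swedish exposure precedes the window. The month of the Finnish 2020 survey is not given. With the year alone, a 2020 tobacco answer cannot be ordered against a 2020 diagnosis from the listed variables.

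Norway's share of pooled participants is at most (280,000 + 9,000) / (424,386 + 44,199 + 289,000) = 289,000 / 757,585 = 38.1%. This is an upper bound, because the number who answered the questionnaires is not stated.

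**2. Illustration of size (all inputs assumed)**

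Let p be the prevalence of use before infection, q the share of infected users who stop before answering, and b the share of uninfected users who stop. With a true RR of 1, a rare outcome, and all answers given after infection:

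Observed RR = [p(1−q) / (1−p(1−q))] / [p(1−b) / (1−p(1−b))]

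At p = 0.10:

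- q = 0.20, b = 0: (0.08/0.92) / (0.10/0.90) = 0.78
- q = 0.20, b = 0.10: (0.08/0.92) / (0.09/0.91) = 0.88
- q = 0.20, b = 0.20: 1.00
- q = 0.10, b = 0.20: (0.09/0.91) / (0.08/0.92) = 1.14

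The 0.88 case changes little with prevalence (0.88 at p = 0.05, 0.87 at p = 0.15).

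Pooled RR = exp(w × ln 0.879), with w the Norwegian weight on the log scale and a null RR elsewhere:

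- w = 0.10: 0.99
- w = 0.20: 0.97
- w = 0.40: 0.95

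For scale, the Background cites an RR of 0.67. To produce that within Norway by this mechanism alone, with b = 0.10, q would have to be 0.38.

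**Poisson against Cox.** HR = ln(1 − 0.67r) / ln(1 − r), with r the risk in non-users. An RR of 0.67 corresponds to an HR of 0.669 at r = 1% and 0.664 at r = 5%. The change of model matters little for rare outcomes.

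**The case against.** **The plan already handles it.** The second sensitivity analysis restricts to prospective data and names information bias as its reason, so a reader who infers that the authors overlooked the issue goes too far. This stands as mitigation. It does not change the primary estimate. Because it changes the countries and the model together, a difference from the primary result could not be put down to exposure timing alone.

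**Smoking is not snus.** A reader might infer that all Norwegian smoking status follows the outcomes, since the date variable refers to the latest assessment. The documents do not support that. The variable describes a date, the exposure definition names no questionnaire, and the June 2020 answer precedes the July to December outcomes. For smoking the established defect is the absence of a rule. Nor does the year-only format show that the countries lack full dates, because harmonisation aimed at a minimum common format.

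**Bias towards protection is not shown.** A reader might infer a falsely protective result. The documents give no stopping rates, and the illustration goes either way. The pooled shift is modest even when all Norwegian answers are taken after infection, which is a worst case for smoking.

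**Removing Norway from snus has a price.** The harmonisation rule admits to the pooled analysis only variables held by at least two countries, and the documents do not say whether Finland holds snus data. Without Norway, the snus estimate might rest on Sweden alone. Under assumed weights of 10, 20 or 40%, full removal would widen the interval by 1/√(1−w) − 1 = 5, 12 or 29%. This objection stands, and it argues for reporting both versions.

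**Earlier is not always better.** Swedish status may date from 2015, so correct time order can come with out-of-date exposure. That is fair, but it does not justify exposure recorded after the outcome without a rule.

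**Conclusion.** The point holds with high confidence for snus: following the plan as written puts exposure recorded after all outcomes into the primary model, and Norway can supply no snus-classified deaths from the questionnaire named. For smoking it holds in narrower form: the defining answer is unspecified, even the June 2020 answer follows four full months of outcomes, and nothing requires exposure to come first. Finland 2020 needs the same clarification.

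The size and direction of bias are unknown. The range of 0.99 to 0.95 for a null pooled RR rests on assumed prevalence, stopping rates and weights, and is an illustration only. If tobacco data from earlier cohort waves were used, the extent would differ, but the plan does not say so. This should be fixed before analysis; it does not invalidate the study.

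**What to change.** 1. **Smoking, primary analysis.** Require exposure to be recorded before any counted outcome. For Norway, define smoking by the June 2020 answer, exclude people already diagnosed, and count only dated outcomes after that answer. Apply the same rule to Finland 2020 or leave that wave out. Carry the rule into the Sweden and Norway sensitivity analysis.
2. **Dates.** Add the full date of tobacco assessment to Date variables for Norway and Finland 2020.
3. **Snus.** Report the pooled estimate with and without Norway side by side, and state that Norwegian snus was recorded after the outcomes. Draw no snus conclusion that depends on Norway alone, and do not use Norway for snus and death.
4. **Like-for-like check.** Fit the primary Poisson RR model to Sweden plus Finland 2018 and 2019, alongside the planned Cox model.
5. **Norwegian case definition.** Reconcile Data Sources (PCR only) with Outcome Variables (PCR or antibodies). Antibody positives do not date the infection, so they cannot satisfy a time-order rule.

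**Cost.** SAP wording, one date variable (assumed to be held by each country) and one extra model fit. Norwegian events before the June answer, and people who answered only in January 2021, leave the primary smoking analysis. If half the Norwegian information is lost, the interval for the pooled log RR widens by the factor 1/√(1 − 0.5w): 1.026, 1.054 or 1.118 at w = 0.10, 0.20 or 0.40, that is about 3, 5 or 12%. Both the share lost and the weights are assumed. Norway also drops out of the early stratum in the time-period analysis.

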### ***Exposure Variables***

Tobacco use (cigarette smoking and/or snus use) will be considered as exposure as follows:

#### *1. Current Cigarette Smoking*

Participants will be grouped as current cigarette smokers if they reported daily or occasional smoking. A categorical variable for current smoking status will be created (non-current smoker = 1, current daily or occasional smokers=2)

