#### *2. Current amount cigarette smoked/day*

Current amount of cigarette smoked/day will be included as a continuous variable. Also a categorical variable of the originally reported average daily consumption will be created as follows: no smoking, 10 cigarettes per day (CPD) or less; 11-20 CPD; more than 20 CPD.

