### *3. Current Snus use*

Participants will be grouped as current snus users if they reported daily or occasional snus use. A categorical variable for current snus use will be created (non-current snus user= 1, current daily or occasional snus user= 2)

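### Every tobacco contrast uses a reference group that merges never and former users, and no planned analysis uses never-users, so the RR for current use may be biased downward if former users carry higher adjusted risk

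*Combined protocol and SAP*

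**What the plan says.** All three exposure variables in the combined protocol and SAP compare current use with everything else.

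- Smoking (Exposure Variables, item 1): "A categorical variable for current smoking status will be created (non-current smoker = 1, current daily or occasional smokers=2".
- Snus (item 3): "non-current snus user= 1, current daily or occasional snus user= 2".
- Cigarettes per day, CPD (item 2): the categories are "no smoking, 10 cigarettes per day (CPD) or less; 11-20 CPD; more than 20 CPD". The variable is defined on the amount currently smoked, so a person who has stopped falls in the first category.

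Under Data Sources, the Swedish dental records hold more than this: "At each health check-up smoking and snus use are ascertained as past use, current use, and amount of current use". For Norway that section mentions current smoking, with snus and other tobacco asked about in January 2021. For Finland it does not say whether past use was asked.

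The same section limits the pooled analysis to variables available in at least two countries and harmonises to the minimum common format. Past use is not among the covariates. The Statistical analysis section plans stratification by sex, age, education and time period. It also plans three sensitivity analyses: added confounders, prospectively collected data only, and competing risks for death. None has a former-user category or a never-user reference, and the plan does not comment on the mixed reference group.

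**The concern.** The Background says that earlier studies reported an apparent protective effect of tobacco, and attributes much of this to selection bias and confounding. The study is meant to do better. A reference group that contains former users can push the estimate in the disputed direction. People who stop smoking because of lung or heart disease are coded with lifelong never-smokers, and if their risk of a severe outcome is raised, they raise the risk in the reference.

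The snus contrast, on which the plan relies to separate a possible role of nicotine, has the same structure, although the documents give no reason to expect a particular risk in former snus users.

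Without an analysis that separates former from never users, a reader who sees an RR below 1 cannot judge how much of it comes from the composition of the reference group.

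**Working it through.** The plan states no sample size, target RR, event count or share of former users, so there is no figure of its own to reproduce.

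**Formula.** Let f be the share of former users among non-current users, and let RR_current and RR_former each be relative to never-users. The reference risk, in units of the never-user risk, is (1 − f) + f × RR_former = 1 + f(RR_former − 1). Hence

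RR_observed = RR_current / [1 + f(RR_former − 1)].

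This is the crude relation. The planned RR is adjusted for covariates, so the RR_former that matters is the one remaining after adjustment.

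**True RR of 1.00** (f and RR_former are assumptions):

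| f | RR_former | 1 + f(RR_former − 1) | RR_observed |
|---|---|---|---|
| 0.2 | 1.2 | 1.04 | 0.96 |
| 0.3 | 1.4 | 1.12 | 0.89 |
| 0.4 | 1.6 | 1.24 | 0.81 |

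Over a wider range, f 0.1–0.4 and RR_former 1.1–2.0, the result runs from 1/1.01 = 0.99 to 1/1.40 = 0.71. With RR_former = 1 there is no shift. With RR_former = 0.9 the shift reverses, to 1/0.99 = 1.01 up to 1/0.96 = 1.04.

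**True harm.** RR_observed is below 1 only if RR_current < 1 + f(RR_former − 1).

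- True 1.10, f = 0.3, RR_former = 1.5: 1.10/1.15 = 0.96, a reversal.
- True 1.20, f = 0.2, RR_former = 1.3: 1.20/1.06 = 1.13, attenuated only.
- True 1.50 at the extreme of the wider range, f = 0.4 and RR_former = 2.0: 1.50/1.40 = 1.07, still above 1.

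**The cited RR of 0.67 for infection (Background).** To produce it from a true 1.00, RR_former must equal 1 + (1/0.67 − 1)/f, which is 2.23 at f = 0.4 and 5.93 at f = 0.1.

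**Sampling error.** Suppose, for illustration only, 4,000 admissions with 10% in smokers. The 95% half-width on the log RR is 1.96 × √(1/400 + 1/3,600) = 0.103. The log shifts in the three table rows are 0.039, 0.113 and 0.215. The first is less than half the half-width, the second is about equal to it, and the third is about twice it.

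**Share of the data with past use.** Sweden contributes 424,386 of 424,386 + 44,199 = 468,585 Swedish and Finnish records (90.6%). If the full Norwegian cohort sizes of 280,000 and 9,000 are added, it contributes 424,386/757,585 = 56%.

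**The case against.** Several objections carry weight.

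- **Harmonisation.** If past use exists only in Sweden, the two-country rule excludes it from the pooled analysis. This stands as an explanation of the primary coding. It does not explain the absence of a sensitivity analysis, since two of the three planned ones already use country subsets (Sweden with Norway; Sweden with Finland 2018 and 2019).
- **Adjustment.** The primary model adjusts for age and other covariates, which may remove part of any excess risk in former users. The Sweden–Norway sensitivity analysis adds tobacco-related comorbidity, which bears directly on quitting because of illness. Both help in part; neither separates former from never users.
- **Dose gradient.** In the categorical CPD analysis a mixed zero group scales every smoking category by the same factor, so comparisons among the three smoking levels are unaffected. This stands. Only the comparisons with the zero group are affected.
- **Earlier country studies.** Setting and study design says that country-specific data have already been analysed. A Swedish never/former/current analysis may exist there, but this plan does not refer to one.
- **Limits of the remedy.** Moving ill quitters out of the reference leaves current smokers as those well enough to continue, so current versus never can still be biased downward. This stands, and it rules out making the never-user result the sole test.

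A reader might also infer that the coding will produce an RR below 1, or that it accounts for the published 0.67. The documents support neither. The first needs RR_former above 1 and a true RR below the threshold shown above. The second needs an RR_former of at least 2.23 over the range of f considered, for infection, an outcome for which no reason is given to expect raised risk in former users.

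**Conclusion.** The concern holds as a conditional one. The mixed reference is certain from the text, as are the availability of past use in Sweden and the absence of a never-user analysis. The direction of bias is downward if former users have a higher adjusted risk than never-users. Its size is not known: 0.96 to 0.81 for a true 1.00 rests on assumed values of f (20–40%) and RR_former (1.2–1.6), before covariate adjustment. A null or modest harm could look protective, while larger harms would be attenuated but not reversed. The mechanism is more plausible for admission, ICU care and death than for infection.

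It is tempting to add that the bias exceeds sampling error. The documents contain no event counts, and under the illustrative counts above the answer changes across the assumed range, so that claim cannot be made.

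The planned current versus non-current contrast remains estimable and valid under that description. What is missing is the check needed before an RR below 1 is interpreted as lower risk in tobacco users.

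**What to change.** Keep the pooled current/non-current model as primary, and describe its contrast as current versus non-current use. Then:

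1. Add a sensitivity analysis in Sweden, and in any other country that holds past use, with a three-level variable (never, former, current) for smoking and for snus. Use never-users as the reference and never-smokers as the CPD zero group.
2. Report former-use and current-use RRs for infection, admission, ICU care and death beside the current/non-current RR from the same country subset. A change of reference is then not confused with a change of country.
3. State that an RR below 1 will not be interpreted as lower risk in tobacco users without reporting whether it persists against never-users. State also that this check does not remove all selection from quitting because of illness.

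The cost is one derived variable per product and one further set of model runs on data already recorded in Sweden. The analysis covers fewer countries and its intervals are somewhat wider. The narrower reference alone costs little. With the illustrative 4,000 admissions, f = 0.3 and RR_former = 1.4, never-smokers hold 3,600 × 0.7/1.12 = 2,250 of the reference events, and the half-width goes from 0.103 to 1.96 × √(1/400 + 1/2,250) = 0.106. The loss from dropping countries comes on top and cannot be computed from the documents.
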